	Wk 1P	Wk 3P	Wk 5P	Wk 7P	Wk 9P	Wk 11P	Wk 13P	Wk15P	Wk 17P	Wk19P	Wk 21P	Wk 23P	Wk 25P	Wk 27P	Wk 29P	Wk 31P	Wk 33P	Wk 35P	Wk 37P			
Dose Number	1	2	3	4	5	6	7	8	9	10	11	12	13	14	15	16	17	18	19			
Participants previously on placebo: Dose Level (mg)	120	pcb	120	pcb	120	pcb	255	pcb	255	pcb	255	pcb	510	pcb	510	pcb	510	pcb	510			
Participants previously on placebo: Injections (mL)	1 × 0.8 A + 2 × 1.7 pcb	2 × 1.7 pcb	1 × 0.8 A + 2 × 1.7 pcb	2 × 1.7 pcb	1 × 0.8 A + 2 × 1.7 pcb	2 × 1.7 pcb	1 × 1.7 A + 1 × 1.7 pcb	2 × 1.7 pcb	1 × 1.7 A + 1 × 1.7 pcb	2 × 1.7 pcb	1 × 1.7 A + 1 × 1.7 pcb	2 × 1.7 pcb	2 × 1.7 A	2 × 1.7 pcb	2 × 1.7 A	2 × 1.7 pcb	2 × 1.7 A	2 × 1.7 pcb	2 × 1.7 A			
Participants previously on active treatment: Dose Level (mg)	510	510	510	510	510	510	510	510	510	510	510	510	510	510	510	510	510	510	510			
Participants previously on active treatment: Injections (mL)	1 × 0.8 pcb + 2 × 1.7 A	2 × 1.7 A	1 × 0.8 pcb + 2 × 1.7 A	2 × 1.7 A	1 × 0.8 pcb + 2 × 1.7 A	2 × 1.7 A	2 × 1.7 A	2 × 1.7 A	2 × 1.7 A	2 × 1.7 A	2 × 1.7 A	2 × 1.7 A	2 × 1.7 A	2 × 1.7 A	2 × 1.7 A	2 × 1.7 A	2 × 1.7 A	2 × 1.7 A	2 × 1.7 A			
Limited physical examination													x ^B								x	
Weight	x ^B												x ^B									x
Vital signs	x ^B		x ^B		x ^B		x ^B		x ^B		x ^B		x ^B							x ^B		x
Concomitant medications ⁱ	x ^B		x ^B		x ^B		x ^B		x ^B		x ^B		x ^B		x ^B		x ^B		x ^B		x ^B	x
Adverse events ⁱ	x ^B		x ^B		x ^B		x ^B		x ^B		x ^B		x ^B		x ^B		x ^B		x ^B		x ^B	x
Urine pregnancy test	x ^B																					x
MRI scan ^{e, f}	x ^B												x ^B								x ^B	x
Amyloid PET scan ^{i, k, l}	x																					

Table 6 Schedule of Activities: Post-Progression Dose Escalation with Q2W Study Drug Administration Frequency; Dosing Weeks 1P–37P (cont.)

Assessment / Procedure	Dose Escalation Period ^{a,1}																			Unsch Visit ^b
	Wk 1P	Wk 3P	Wk 5P	Wk 7P	Wk 9P	Wk 11P	Wk 13P	Wk 15P	Wk 17P	Wk 19P	Wk 21P	Wk 23P	Wk 25P	Wk 27P	Wk 29P	Wk 31P	Wk 33P	Wk 35P	Wk 37P	
Dose Number	1	2	3	4	5	6	7	8	9	10	11	12	13	14	15	16	17	18	19	
Participants previously on placebo: Dose Level (mg)	120	pcb	120	pcb	120	pcb	255	pcb	255	pcb	255	pcb	510	pcb	510	pcb	510	pcb	510	
Participants previously on placebo: Injections (mL)	1 × 0.8 A + 2 × 1.7 pcb	2 × 1.7 pcb	1 × 0.8 A + 2 × 1.7 pcb	2 × 1.7 pcb	1 × 0.8 A + 2 × 1.7 pcb	2 × 1.7 pcb	1 × 1.7 A + 1 × 1.7 pcb	2 × 1.7 pcb	1 × 1.7 A + 1 × 1.7 pcb	2 × 1.7 pcb	1 × 1.7 A + 1 × 1.7 pcb	2 × 1.7 pcb	2 × 1.7 A	2 × 1.7 pcb	2 × 1.7 A	2 × 1.7 pcb	2 × 1.7 A	2 × 1.7 pcb	2 × 1.7 A	2 × 1.7 A
Participants previously on active treatment: Dose Level (mg)	510	510	510	510	510	510	510	510	510	510	510	510	510	510	510	510	510	510	510	510
Participants previously on active treatment: Injections (mL)	1 × 0.8 pcb + 2 × 1.7 A	2 × 1.7 A	1 × 0.8 pcb + 2 × 1.7 A	2 × 1.7 A	1 × 0.8 pcb + 2 × 1.7 A	2 × 1.7 A	2 × 1.7 A	2 × 1.7 A	2 × 1.7 A	2 × 1.7 A	2 × 1.7 A	2 × 1.7 A	2 × 1.7 A	2 × 1.7 A	2 × 1.7 A	2 × 1.7 A	2 × 1.7 A	2 × 1.7 A	2 × 1.7 A	2 × 1.7 A
Tau PET scan ^{i,k,l}	x																			
CSF sampling ^{l,m}	x ^B																			
C-SSRS	x ^B												x ^B							x

ADA = anti-drug antibody; ARIA-E = amyloid-related imaging abnormalities – edema/effusion; ARIA-H = amyloid-related imaging abnormalities – hemosiderin deposition; C = in-clinic administration by study staff; CSF = cerebrospinal fluid; CRP = C-reactive protein; C-SSRS = Columbia-Suicide Severity Rating Scale; MN = visit appropriate for home administration by *mobile* nursing professional, where applicable; MRI = magnetic resonance imaging; pcb = placebo; PET = positron emission tomography; PK = pharmacokinetic; Q2W = every 2 weeks; Unsch = unscheduled; Wk = week.

x ^B = before study drug administration; visits may be split over 2 consecutive days.

During the post-progression dose escalation period, all assessments, with the exception of the neuropsychological efficacy assessments, should be performed following the schedule of activities in [Table 6](#) considering the related footnotes (a–m). Following Week 37P, assessments should be continued as per [Table 5](#), with the exception of MRI monitoring, taking into account the time spent on the post-progression dose escalation (i.e., [Table 6](#)). For example, if a participant moved from [Table 5](#) at Week 100, and completed the activities of [Week 37P \(Table 6\)](#), then activities of [Table 5](#) should be resumed starting at Week 138. Early Termination visits should be conducted as detailed in [Table 5](#).

Table 6 Schedule of Activities: Post-Progression Dose Escalation with Q2W Study Drug Administration Frequency; Dosing Weeks 1P–37P (cont.)

- ^a Visit weeks and dose numbers only refer to the 'post-progression dose escalation' period. Visit weeks are labeled 'P' (i.e., post-progression).
- ^b *Visits at Weeks 1P, 5P, 9P, 13P, 17P, 21P, 25P, 29P, 33P, and 37P are defined as 'definitely active dosing' visits when both participant previously on placebo and active treatment receive an active dose of study drug.*
- ^c Scope of the unscheduled visit should include all efficacy assessments if they were missed at the preceding, regularly scheduled efficacy assessments visit. Safety assessments, including physical examinations, must also be included if they were missed at the preceding, regularly scheduled safety assessments visit or as clinically indicated. Unscheduled visits related to the occurrence of ARIA-E or ARIA-H are to follow the PK, ADA and plasma biomarker sampling rules as detailed below.
- ^d Participants should be observed for at least 2 hours after after the first 4 'definitely active doses' (i.e., at Week 1P, Week 5P, Week 9P and Week 13P); the observation time may be reduced to at least 1 hour following all other administrations. Participant or study partner administration is prohibited during the 'post-progression dose escalation' period. Study drug administration by the participant or their study partner may resume after Week 37P following assessment and adequate training, if necessary, by the site. Sites must verify participant/study partner readiness for study drug administration.
- ^e If MRI, 12-lead ECG, metabolic tests, CRP, *PT* serum chemistry and hematology were obtained within 4-weeks of Week 1P, these assessments do not need to be repeated during the Week 1P visit.
- ^f Visits, including PK, ADA and plasma biomarker sampling must take place in-clinic.
A PK sample is to be obtained as soon as practicable (e.g., at an unscheduled visit or the next study visit) following an MRI scan showing new occurrence or worsening of ARIA-E or ARIA-H that meets the discontinuation criteria. An additional plasma exploratory biomarkers sample is to be obtained as soon as practicable (e.g., at an unscheduled visit or the next study visit) following each MRI scan showing ARIA-E until and including ARIA-E resolution (i.e., new, worsened, stable, improved, resolved ARIA-E).
- ^g *During the post-progression dose escalation period, MRIs must be obtained -at minimum- before the first post-progression dose (Week 1P), after the second (Week 25P) and third (Week 37P) dose-escalation steps as detailed in Table 6. Once participants have reached target dose, MRIs must be obtained 4 months, then 10 months, then 16 months after the first target dose, after which annual MRI monitoring frequency can be initiated.*
- ^h *Metabolic tests include hemoglobin A1C, total cholesterol, high-density lipoprotein, low-density lipoprotein, triglycerides, folic acid, vitamin B-12, methylmalonic acid, total thyroxine, free thyroxine, and thyroid-stimulating hormone levels. These tests should be collected as fasting samples (i.e., at least 4 hours after meals).*
- ⁱ Every 4 weeks, except when there is an in-clinic visit, the investigator or an appointed qualified study staff member will have a telephone conversation with the participant and study partner to elicit, in a non-leading way, information on medication errors, adverse events, and changes to concomitant medications that may have occurred in the home setting. Therefore, there will be contact between the study staff and the participant/study partner at least every 4 weeks. The study staff is encouraged to have more frequent calls with a particular participant/study partner if considered appropriate by the investigator. In addition, the participant and study partner must be instructed to contact the investigator and seek approval for continued study drug dosing in the home setting in case of onset of any new symptoms or symptom worsening, new or changed concomitant medications, or medication errors.
- ^j Optional post-baseline amyloid and tau PET scans will be administered until the target number of scans is reached.
- ^k Tau and amyloid PET scheduling window is \pm 14 days. In an exceptional case of tau or amyloid PET scheduling issue the Sponsor must be notified and the scans may be performed up to 3 months after the scheduled assessment. For Early Termination visits, tau and amyloid PET scans should only be obtained if the last scan was > 6 months earlier.

Table 6 Schedule of Activities: Post-Progression Dose Escalation with Q2W Study Drug Administration Frequency; Dosing Weeks 1P–37P (cont.)

- ^l CSF sampling, amyloid and tau PET scans must be repeated prior to the first 'post-progression dose escalation dose administration if the last such assessment occurred > 6 months earlier. This repeat assessment will then replace the next originally scheduled Year 2, Year 3, or Year 4 assessment if this assessment is due in < 6 months. If the last CSF sampling, amyloid and tau PET scan took place ≤ 6 months of the first 'post-progression dose escalation' dose administration, assessments should be continued as per the original schedule of activities (i.e., [Table 5](#)).
- ^m Optional post-baseline CSF sampling will be continued until the target number of samples is reached. Cerebrospinal fluid collection must be performed in the morning (between 8:00 a.m. and noon) to minimize potential diurnal variation of CSF parameters and should be performed prior to dosing.

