- ^f Tau and amyloid PET scheduling window is \pm 14 days. In an exceptional case of tau or amyloid PET scheduling issues the Sponsor must be notified and the scans may be performed up to 3 months after the scheduled assessment. For Early Termination visits, tau and amyloid PET scans should only be obtained if the last scan was > 6 months earlier.
- ^g Optional post-baseline CSF samples will be collected until the target number of samples is reached. Cerebrospinal fluid collection must be performed in the morning (between 8:00 a.m. and noon) to minimize potential diurnal variation of CSF parameters and should be performed prior to dosing. For Early Termination visits, CSF sampling should only be obtained if the last CSF sampling was > 6 months earlier.

Table 3 Schedule of Activities: Post-Progression Dose Escalation with Q1W Study Drug Administration Frequency; Dosing Weeks 1P–37P

Neuropsychological efficacy assessments (i.e., Preclinical Alzheimer's Cognitive Composite-5 [PACC-5], Cognitive Function Instrument acute [CFIa], Amsterdam Instrumental Activities of Daily Living Questionnaire Short Version [A-AIDL-Q-SV], Clinical Dementia Rating [CDR], Alzheimer's disease Clinician Global Impression of Cognitive Function [AD-CGI-S], Alzheimer's disease Participant Global Impression of Cognitive Function [AD-PGI-S], Alzheimer's disease Study Partner Global Impression of Cognitive Function [AD-SPGI-S], EuroQol 5-Dimension, 5-Level Questionnaire [EQ-5D-5L], Geriatric Depression Scale-30 [GDS-30]), and the Diagnostic Classification Form (DCF), should continue as per the original schedule of activities (i.e., [Table 2](#)).

Participants originally randomized to active treatment will continue with gantenerumab 255 mg SC every 1 week (Q1W).

Table 3 Schedule of Activities: Post-Progression Dose Escalation with Q1W Study Drug Administration Frequency; Dosing Weeks 1P–37P (cont.)

Assessment/ Procedure	Dose Escalation Period ^{a, b}																										Unsch Visit ^c	
	Wk 1P	Wk 2P–4P	Wk 5P	Wk 6P–8P	Wk 9P	Wk 10P –12P	Wk 13P	Wk 14P –16P	Wk 17P	Wk 18P –20P	Wk 21P	Wk 22P –24P	Wk 25P	Wk 26P	Wk 27P	Wk 28P	Wk 29P	Wk 30P	Wk 31P	Wk 32P	Wk 33P	Wk 34P	Wk 35P	Wk 36P	Wk 37P			
Dose Number	1	2–4	5	6–8	9	10–12	13	14–16	17	18–20	21	22–24	25	26	27	28	29	30	31	32	33	34	35	36	37			
Participants previously on placebo: Dose Level (mg)	120	pcb	120	pcb	120	pcb	255	pcb	255	pcb	255	pcb	255	pcb	255	pcb	255	pcb	255	pcb	255	pcb	255	pcb	255	pcb	255	

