Participants previously on active treatment: Injections (mL)	1 × 0.8 pcb + 1 × 1.7 A	1 × 1.7 A	1 × 0.8 pcb + 1 × 1.7 A	1 × 1.7 A	1 × 0.8 pcb + 1 × 1.7 A	1 × 1.7 A	1 × 1.7 A	1 × 1.7 A	1 × 1.7 A	1 × 1.7 A	1 × 1.7 A	1 × 1.7 A	1 × 1.7 A	1 × 1.7 A	1 × 1.7 A	1 × 1.7 A	1 × 1.7 A	1 × 1.7 A	1 × 1.7 A	1 × 1.7 A	1 × 1.7 A	1 × 1.7 A	1 × 1.7 A	1 × 1.7 A	1 × 1.7 A	1 × 1.7 A	1 × 1.7 A		
Urine pregnancy test	x ^B																											x	
MRI scan ^{e, f}	x ^B												x ^B															x ^B	x
Amyloid PET scan ^{i, k, l}	x																												
Tau PET scan ^{i, k, l}	x																												
CSF sampling ^{i, m}	x ^B																												
C-SSRS	x ^B																												x

ADA = anti-drug antibody; ARIA-E = amyloid-related imaging abnormalities—edema/effusion; ARIA-H = amyloid-related imaging abnormalities—hemosiderin deposition; C = in-clinic administration by study staff; CSF = cerebrospinal fluid; C-SSRS = Columbia-Suicide Severity Rating Scale; MN = visit appropriate for home administration by *mobile* nursing professional, where applicable; MRI = magnetic resonance imaging; pcb = placebo; PET = positron emission tomography; PK = pharmacokinetic; Q1W = every 1 week; Unsch = unscheduled; Wk = week.

x ^B = before study drug administration; visits may be split over 2 consecutive days.

During the post-progression dose escalation period, all assessments, with the exception of the neuropsychological efficacy assessments, should be performed following the schedule of activities in Table 3 considering the related footnotes (a–m). Following Week 37P, assessments should be continued as per Table 2, with the exception of MRI monitoring, taking into account the time spent on the post-progression dose escalation (i.e., Table 3). For example, if a participant moved from Table 2 at Week 100, and completed the activities of Week 37P (Table 3), then activities of Table 2 should be resumed starting at Week 138. Early Termination visits should be conducted as detailed in Table 2.

Table 3 Schedule of Activities: Post-Progression Dose Escalation with Q1W Study Drug Administration Frequency; Dosing Weeks 1P–37P (cont.)

- ^a Visit weeks and dose numbers only refer to the 'post-progression dose escalation' period. Visit weeks are labeled 'P' (i.e., post-progression).

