8.2.6 Monitoring for Suicidal Ideation and Behavior

Participants should be monitored appropriately and observed closely for suicidal ideation and behavior or any other unusual changes in behavior, especially at the beginning and end of the course of study drug treatment, or at the time of dose changes.

Consideration should be given to discontinuing study drug in participants who experience signs of suicidal ideation or behavior, following a risk assessment.

Study partners, families, and caregivers of participants should be alerted about the need to monitor participants for the emergence of unusual changes in behavior, as well as the emergence of suicidal ideation and behavior and to report such symptoms immediately to the study investigator. Assessment of suicidal ideation and behavior or treatment-emergent suicidal ideation and behavior will be monitored during Study WN42444 with use of the C-SSRS (Posner et al. 2011).

The C-SSRS (<https://www.cssrs.columbia.edu>) is an assessment tool used to assess the lifetime suicidality of a participant (C-SSRS assessment at baseline) as well as any new instances of suicidality (C-SSRS assessments after baseline). The structured interview prompts recollection of suicidal ideation, including the intensity of the ideation, behavior, and attempts with actual or potential lethality. The C-SSRS assessments will be performed as indicated in the schedule of activities (see Section 1.3, Table 1, Table 2, and Table 3 for the QW1 dosing regimen and Table 4, Table 5, and Table 6 for the Q2W dosing regimen).

The assessment will be completed by a certified C-SSRS rater after he or she interviews the participant and their study partner during the study visit.

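### Table 3 (Q1W post-progression) omits the Week 25P C-SSRS that Table 6 (Q2W) schedules, leaving Q1W progressors up to 62 weeks (64 at the end of the study) without a scheduled assessment

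*Combined protocol and SAP*

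**What the plan says.** All of this is in the protocol.

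- **Table 3 (Q1W, post-progression), Section 1.3.** The C-SSRS row is marked at Week 1P and under unscheduled visits; the Week 25P cell is empty. The note below the table says that "all assessments, with the exception of the neuropsychological efficacy assessments, should be performed following the schedule of activities in Table 3".
- **Opening text of Table 3.** It names ten instruments, the last being the DCF: "and the Diagnostic Classification Form (DCF), should continue as per the original schedule of activities", that is, Table 2. The GDS-30 is on that list. The C-SSRS is not.
- **Return to Table 2.** "Following Week 37P, assessments should be continued as per Table 2, with the exception of MRI monitoring". In the worked example a participant leaves Table 2 at Week 100, completes Week 37P, and "then activities of Table 2 should be resumed starting at Week 138".
- **Table 6 (Q2W, post-progression).** It carries the same governing note, but its C-SSRS row is marked at Weeks 1P and 25P as well as unscheduled visits.
- **Tables 1 and 4 (initial escalation).** Both mark the C-SSRS at Weeks 1 and 25.
- **Section 8.2.6.** It asks for close observation of suicidal ideation and behaviour, "especially at the beginning and end of the course of study drug treatment, or at the time of dose changes". For the instrument itself it defers to the tables: "The C-SSRS assessments will be performed as indicated in the schedule of activities".

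Table 7 lists the C-SSRS among the safety endpoints. The weight row shows the same difference: Table 6 has a Week 25P entry and Table 3 does not.

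**The concern.** Four tables cover a dose-escalation period. Three place a C-SSRS about 24 weeks after the first dose, and Table 3 does not. Table 3 governs everything except the listed efficacy instruments until Week 37P. The 6-monthly Table 2 visits that fall inside the escalation are therefore still held for the PACC-5, CDR and GDS-30, but no longer carry a C-SSRS.

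These participants have just had progression to MCI or dementia due to AD confirmed. Those randomised to placebo are being switched to active drug, unless the ongoing Phase III studies fail to show efficacy. Followed exactly, Table 3 lets one regimen go well over the usual interval without a scheduled assessment on a listed safety endpoint, and no section explains why the regimens should differ. At stake is the completeness of suicidality data in Q1W progressors.

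**Working it through.** This is calendar arithmetic on the visit tables.

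**Inputs**
- Table 2 C-SSRS visits in the treatment period after initial escalation: Weeks 53, 79, 105, 131, 157, 183, 211. Spacing is 26 weeks five times, then 211 − 183 = 28. Table 5 uses the same weeks for Q2W.
- Table 3 C-SSRS: Week 1P only. Table 6 C-SSRS: Weeks 1P and 25P.
- Offsets from 1P: 25P is 24 weeks later, 37P is 36 weeks later, and Table 2 resumes 37 weeks later.

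**The protocol's own figure first.** Leaving Table 2 at Week 100 puts 1P at Week 101. Then 37P = 101 + 36 = 137, and Table 2 resumes at 101 + 37 = 138. This matches the stated Week 138.

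**That example, by regimen**
- Q1W: Week 101, then the first listed visit at or after 138, which is 157. Gap = 157 − 101 = 56 weeks. The Table 2 visits at Weeks 105 and 131 fall inside the escalation and supply no C-SSRS.
- Q2W: 25P = 101 + 24 = 125. Gaps = 125 − 101 = 24 weeks and 157 − 125 = 32 weeks.

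**General Q1W gap.** With 1P at study week S, gap = (first listed visit at or after S + 37) − S. Working through every S from 54 gives:

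| Case | Example | Gap (weeks) |
|---|---|---|
| Minimum when Table 2 resumes by Week 211 | S = 68, next 105 | 105 − 68 = 37 |
| Maximum, next visit before Week 211 | S = 121, next 183 | 183 − 121 = 62 |
| Maximum, next visit Week 211 | S = 147, next 211 | 211 − 147 = 64 |
| Just below that | S = 148, next 211 | 211 − 148 = 63 |
| Entry after Week 174 | S = 175 or later; Table 2 would resume at 212 or later | 211 − 175 = 36 or less |

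The last row assumes that the Week 211 final assessment is held even if it falls inside the escalation. That fits the fixed 211-week treatment period.

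**A likelier entry time.** Progression is confirmed at a 6-monthly visit, but the lag from confirmation to 1P is not stated. Assuming 1 to 12 weeks after such a visit, the next C-SSRS is 52 weeks after that visit (54 when it is Week 211):
- next visit before Week 211: 52 − 12 = 40 to 52 − 1 = 51 weeks;
- next visit Week 211, entry after the Week 157 visit: 54 − 12 = 42 to 54 − 1 = 53 weeks;
- entry after the Week 183 visit: 28 − 12 = 16 to 28 − 1 = 27 weeks.

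**If the Q1W row matched the Q2W row (illustration).** The first interval would be 24 weeks. The second would run from 37 − 24 = 13 to 62 − 24 = 38 weeks, or 64 − 24 = 40 when the next visit is Week 211.

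**Could the missing mark be a text-reading loss?** Unlikely. In Table 3 the MRI, limited physical examination, ECG, PK and laboratory rows all keep their Week 25P marks. Other cells of these tables are visibly damaged in the extracted text, so the cell should still be checked against the PDF.

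**The case against.** The best defence is that other monitoring continues, and that is right. Table 3 allows a C-SSRS at unscheduled visits, and its notes require safety assessments there when clinically indicated. Contact is at least every 4 weeks, the GDS-30 continues at the 6-monthly visits, and Section 8.2.6 asks for general observation and prompt reporting by study partners. None of these is a scheduled C-SSRS, however. The 4-weekly calls are defined around medication errors, adverse events and concomitant medication.

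Three stronger readings are tempting, and the documents do not support them.

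- **That Section 8.2.6 requires a C-SSRS at Week 25P because the dose changes.** Its reference to dose changes concerns observation, and it leaves C-SSRS timing to the tables. In Table 3 the injection is 255 mg before and after Week 25P; for former placebo participants only the interval between active doses shortens, and those already on gantenerumab have no change. The rise to 255 mg at Week 13P (Week 13 in the initial escalation) has no C-SSRS in any of the four tables.
- **That safety results are biased between arms.** Both randomised arms within a regimen follow the same table.
- **That a planned Q1W-versus-Q2W safety comparison is compromised.** Sections 9.3 and 9.4.4 plan descriptive safety summaries by treatment received, and no comparison by regimen is planned.

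It is also fair to say that Table 6 does not hold to 26 weeks: its second interval can reach 38 or 40. And the group affected may be small. Q2W is the default regimen, only confirmed progressors on target dose enter Table 3, and the protocol gives no expected number.

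**Conclusion.** The discrepancy is real and should be corrected. As written, Q1W progressors have no scheduled C-SSRS for 37 to 62 weeks, up to 64 when the next visit is Week 211, against 26 to 28 weeks on uninterrupted Table 2. Entrants after Week 174 have 36 weeks or less. In the protocol's own example the figure is 56 weeks, where Q2W participants have 24 and 32.

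The consequence is limited to reduced scheduled ascertainment of a listed safety endpoint in one subgroup, on a regimen that participants choose themselves. It does not touch the primary analysis or the balance between arms, and it does not mean that suicidality goes unmonitored.

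The conclusion rests on reading the Table 3 row as printed, on the C-SSRS being outside the listed instruments that stay on Table 2, and on visits falling at their nominal weeks.

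**What to change.** Reconcile the C-SSRS rows of Tables 3 and 6 with each other and with Section 8.2.6. Either give both regimens the same post-progression C-SSRS schedule, or state why they differ. Settle the Week 25P weight entries in the same edit. Which schedule is right is for the sponsor to decide.

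As a guide to cost, aligning Table 3 to Table 6 would mean one table cell, the matching visit set-up in data capture, and one interview at a visit that is already in-clinic, only for Q1W participants who progress. The longest gap would fall from 62 to 38 weeks (64 to 40 when the next visit is Week 211). Keeping the difference would cost a sentence of justification in Section 8.2.6 or in the notes to Table 3.
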